3.5 Discontinuation of subjects following any treatment with study drug

Subjects MUST discontinue investigational product (and non-investigational product at the discretion of the investigator) for any of the following reasons:

- Subject's request to stop study treatment
- Any clinical adverse event (AE), laboratory abnormality or intercurrent illness which, in the opinion of the investigator, indicates that continued participation in the study is not in the best interest of the subject
- Termination of the study by Bristol-Myers Squibb (BMS)
- Loss of ability to freely provide consent through imprisonment or involuntarily incarceration for treatment of either a psychiatric or physical (eg, infectious disease) illness
- Additional protocol specific reasons for discontinuation [Section 4.5.5](#) and [Section 4.5.3](#)

In the case of pregnancy, the investigator must immediately notify the BMS Medical Monitor/designee of this event. In most cases, the study drug will be permanently discontinued in an appropriate manner. If the investigator determines a possible favorable benefit/risk ratio that warrants continuation of study drug and it is allowed by local regulations, a discussion between the investigator and the BMS Medical Monitor/designee must occur.

All subjects who discontinue study drug should comply with protocol specified follow-up procedures as outlined in [Table 5.1-3](#). The only exception to this requirement is when a subject

withdraws consent for all study procedures including post-treatment study follow-up or loses the ability to consent freely (ie, is imprisoned or involuntarily incarcerated for the treatment of either a psychiatric or physical illness).

If study drug is discontinued prior to the subject's completion of the study, the reason for the discontinuation must be documented in the subject's medical records and entered on the appropriate case report form (CRF) page.

3.6 Post Study Drug Study Follow up

In this study, overall survival is a key endpoint of the study. Post study follow-up is of critical importance and is essential to preserving subject safety and the integrity of the study. Subjects who discontinue study drug must continue to be followed for collection of outcome and/or survival follow-up data as required and in line with [Table 5.1-3](#) until death, withdrawal of consent, lost to follow-up or the conclusion of the study.

In addition, subjects who discontinue study therapy by proceeding to allogeneic SCT or ASCT will require tumor assessment (CR or non-CR) by the investigators according to the Lugano Classification 2014 (DLBCL/PTCL) and consensus Global Response Score (CTCL) on day 100, at 6 months, 1 year and every year thereafter from the date of stem cell infusion until the first non-CR after SCT is documented. For the subjects who discontinue study therapy by proceeding to allogeneic SCT, documentation of acute and chronic GVHD will be simultaneously collected see [Appendix 5](#) for more details.

Subjects who discontinue study drug may continue to be followed. BMS may request that survival data be collected on all *treated* subjects outside of the 3 month specified visit schedule. At the time of this request, each subject will be contacted to determine their survival status unless the subject has withdrawn consent for all contact.

3.6.1 Withdrawal of Consent

Subjects who request to discontinue study drug will remain in the study and must continue to be followed for protocol specified follow-up procedures. The only exception to this is when a subject specifically withdraws consent for any further contact with him/her or persons previously authorized by subject to provide this information. Subjects should notify the investigator of the decision to withdraw consent from future follow-up **in writing**, whenever possible. The withdrawal of consent should be explained in detail in the medical records by the investigator, as to whether the withdrawal is from further treatment with study drug only or also from study procedures and/or post treatment study follow-up, and entered on the appropriate CRF page. In the event that vital status (whether the subject is alive or dead) is being measured, publicly available information should be used to determine vital status only as appropriately directed in accordance with local law.

3.6.2 Lost to Follow-Up

All reasonable efforts must be made to locate subjects to determine and report their ongoing status. This includes follow-up with persons authorized by the subject as noted above. Lost to follow-up

is defined by the inability to reach the subject after a minimum of three documented phone calls, faxes, or emails as well as lack of response by subject to one registered mail letter. All attempts should be documented in the subject's medical records. If it is determined that the subject has died, the site will use permissible local methods to obtain the date and cause of death.

If investigator's use of third-party representative to assist in the follow-up portion of the study has been included in the subject's informed consent, then the investigator may use a Sponsor-retained third-party representative to assist site staff with obtaining subject's contact information or other public vital status data necessary to complete the follow-up portion of the study. The site staff and representative will consult publicly available sources, such as public health registries and databases, in order to obtain updated contact information. If after all attempts, the subject remains lost to follow-up, then the last known alive date as determined by the investigator should be reported and documented in the subject's medical records.

4 STUDY DRUG

Study drug includes both Investigational [Medicinal] Product (IP/IMP) and Non-investigational [Medicinal] Product (Non-IP/Non-IMP) and can consist of the following:

Table 4-1: Study Drugs for CA209436

Product Description / Class and Dosage Form	Potency	IP/Non-IMP	Blinded or Open Label	Packaging/ Appearance	Storage Conditions (per label)
BMS-936558-01 Solution for Injection*	100 mg (10 mg/mL)	IP	OPEN LABEL	Clear to opalescent colorless to pale yellow liquid. May contain particles.	2-8°C. Protect from light and freezing.
Brentuximab Vedotin Powder for Injection	50mg	IP	OPEN LABEL	White to off-white lyophilized preservative-free cake or powder in a single-use vial for reconstitution.	2-8°C. Protect from light.

*May be labeled as either “BMS-936558-01” or “Nivolumab”.

Premedications or medications used to treat infusion-related reactions should be sourced by the investigative sites if available and permitted by local regulations

4.1 Investigational Product

An investigational product, also known as investigational medicinal product in some regions, is defined a pharmaceutical form of an active substance or placebo being tested or used as a reference in a clinical study, including products already with a marketing authorization but used or assembled (formulated or packaged) differently than the authorized form, or used for an unauthorized indication, or when used to gain further information about the authorized form.

The investigational product should be stored in a secure area according to local regulations. It is the responsibility of the investigator to ensure that investigational product is only dispensed to study subjects. The investigational product must be dispensed only from official study sites by authorized personnel according to local regulations.

In this protocol, investigational products are:

- Nivolumab (BMS-936558)
- Brentuximab Vedotin

4.2 Non-investigational Product

Other medications used as support or escape medication for preventative, diagnostic, or therapeutic reasons, as components of the standard of care for a given diagnosis, may be considered as non-investigational products.

Not applicable for this study.

4.3 Storage and Dispensing

The product storage manager should ensure that the study drug is stored in accordance with the environmental conditions (temperature, light, and humidity) as determined by BMS. If concerns regarding the quality or appearance of the study drug arise, the study drug should not be dispensed and contact BMS immediately.

Study drug not supplied by BMS will be stored in accordance with the package insert.

Investigational product documentation (whether supplied by BMS or not) must be maintained that includes all processes required to ensure drug is accurately administered. This includes documentation of drug storage, administration and, as applicable, storage temperatures, reconstitution, and use of required processes (eg, required diluents, administration sets).

4.3.1 Brentuximab Vedotin

Brentuximab vedotin will be administered every 21 (q 3 weeks) days by IV infusion given over approximately 30 minutes. In the absence of infusion-related reactions, the infusion rate for all subjects should be calculated in order to achieve a 30 minute infusion period. Brentuximab vedotin must not be administered as an IV push or bolus nor mixed with other medications. Brentuximab vedotin will be administered first as a 30 minute infusion followed by a minimum 30 minute rest prior to the nivolumab infusion.

Dosing is based on subject's actual body weight. Doses must be adjusted for subjects who experience a $\geq 10\%$ change in weight from baseline. Other dose adjustments for changes in body weight are permitted per institutional standard. An exception to weight-based dosing is made for subjects weighing greater than 100 kg; doses will be based on 100 kg for these individuals. Rounding is permissible within 5% of the nominal dose.

Refrigeration should be set at 2–8°C for storage of vials and solutions containing brentuximab vedotin. The controlled location must be accessible only to the pharmacist, the investigator, or a designated person. Brentuximab vedotin does not contain preservatives; therefore, opened and reconstituted vials of brentuximab vedotin should be used as soon as possible. If not used immediately, the in-use storage should not be longer than 24 hours. It is recommended that brentuximab vedotin vials and solutions be protected from direct sunlight until the time of use. Reconstituted vials and solutions must not be shaken.

Drug product vials may be labeled as brentuximab vedotin, the United States adopted name (USAN) and the International Nonproprietary Name (INN), or as SGN 35, the compound code; the 2 names can be used interchangeably.

Brentuximab vedotin vials are provided via single-use containers. Any partially used vials or diluted dosing solutions should be discarded using appropriate institutional drug disposal procedures.

Brentuximab vedotin should be reconstituted with 10.5mL of Sterile Water for Injection, United States Pharmacopeia (USP) or equivalent (see Pharmacy Binder for details) for a final concentration of 5mg/mL. The vial should be gently swirled until the contents are completely dissolved. The vial must not be shaken. The reconstituted drug product should be inspected visually for any particulate matter and discoloration.

The required volume of reconstituted drug product should be diluted into an infusion bag. The bag should be gently inverted to mix the solution. The bag must not be shaken. Prior to administration, the reconstituted and diluted drug product should be inspected visually for any particulate matter and discoloration.

Detailed drug preparation and drug accountability instructions for brentuximab vedotin are provided in the Pharmacy Binder.

4.3.2 Nivolumab

Nivolumab will be administered every 21 days (q 3weeks) by IV infusion given over approximately 30 minutes. Nivolumab (BMS-936558) vials must be stored at a temperature of 2°C to 8°C and should be protected from light and freezing. If stored in a glass front refrigerator, vials should be stored in the carton. Recommended safety measures for preparation and handling of nivolumab include laboratory coats and gloves.

For details on prepared drug storage and use time of nivolumab under room temperature/light and refrigeration, please refer to the BMS-936558 (nivolumab) IB section for “Recommended Storage and Use Conditions” and/or pharmacy reference sheets.

At the end of the infusion, flush the line.

For both study drugs, infusion-related supplies (eg, IV bags, in-line filters, 0.9% NaCl solution) will not be supplied by the sponsor and should be purchased locally if permitted by local regulations.

Please refer to the current version of the IB and/or pharmacy reference sheets for complete storage, handling, dispensing, and infusion information for BMS-936558 (nivolumab).

4.4 Method of Assigning Subject Identification

After the subject's initial eligibility is established and informed consent has been obtained, the subject must be enrolled into the study by calling an IVRS to obtain the subject number. Every subject that signs the informed consent form must be assigned a subject number in IVRS. Specific instructions for using IVRS will be provided to the investigational site in a separate document.

The investigator (or designee) will register the subject for enrollment by following the enrollment procedures established by BMS. The following information is required for enrollment:

- Date of informed consent
- Date of birth
- Gender at birth
- Lymphoma Disease Diagnosis (DLBCL, PTCL, CTCL, PMBL, MGZL)

A separate call will need to be placed to assign eligible subjects their first treatment once the tumor tissue submitted to the central laboratory has gone through the quality assessment and the information is available in the IVRS.

4.5 Selection and Timing of Dose for Each Subject

There will be 2 parts to this study. During the Dose Evaluation Phase (Cohort A) six eligible subjects will be enrolled and treated with brentuximab vedotin (IV) 1.8 mg/kg as the starting dose and may be reduced to 1.2 mg/kg if toxicities described in [Table 4.5.3-1](#) are observed. Subjects enrolled to Cohort A will be treated with a combination of brentuximab vedotin and nivolumab 240 mg flat dose (IV) of every 3 week cycle. In cycle 1, brentuximab vedotin will be administered on day 1 where as nivolumab will be administered on day 8. Subsequent to cycle 1, both drugs will be administered on the first day of the new cycle. Brentuximab vedotin will be administered first as a 30-minute infusion followed by a minimum 30-minute rest. Nivolumab will be then be administered as a 30-minute infusion

The starting dose of brentuximab vedotin 1.8 mg/kg is to be given over approximately 30 minutes intravenously. In the absence of infusion related reaction, the infusion rate for all subjects should be calculated in order to achieve a 30-minute infusion period. Dosing calculations should be based on the subject's actual body weight. If the subject's weight on the day of dosing differs by > 10% from the previous weight used to calculate the required dose, a corrected dose must be recalculated. Other dose adjustments for changes in body weight are permitted per institutional standard. All

doses should be rounded to the nearest milligram. Brentuximab vedotin may be reduced to 1.2mg/kg if toxicities described in [Table 4.5.3-1](#) are observed. The Cohort B will open with a proposed dosing regimen with cycle duration of 21 days (3 weeks). Brentuximab vedotin will be administered based on the dose identified in Cohort A (1.8 mg/kg or 1.2 mg/kg) and nivolumab will be given over 30 min intravenously at a 240 mg flat dose.

An exception to weight-based brentuximab vedotin dosing is made for subjects weighing greater than 100 kg; doses will be based on 100kg for these individuals. Rounding is permissible within 5% for the nominal dose.

There will be no dose escalations or reductions of nivolumab allowed. There are no premedications recommended for nivolumab on the first cycle. If an acute infusion reaction is noted, subjects should be managed according to [Section 4.5.6](#).

First dose of nivolumab will be administered on Cycle 1 Day 8, which is only 2 weeks away from Cycle 2 Day 1. For safety reasons, subjects may be dosed no less than 12 days between doses. For all other cycles, treatment is to occur within 3 days of the scheduled dosing date. Dose given after the 3 day window is considered a dose delay. Treatment may be delayed for up to a maximum of 6 weeks from the previous dose. Refer to [Section 4.5.4](#) for further details.

Subjects will be monitored continuously for AEs while on study. Treatment modifications (eg, dose delay, interruption or discontinuation) will be based on specific laboratory and AE criteria (further details described in [Section 4.5.3](#) and [Section 4.5.4](#)).

4.5.1 Dose Evaluation Phase: (Cohort A)

The Dose Evaluation Phase (Cohort A) will include a dose limiting toxicity (DLT) evaluation for the dose level of brentuximab vedotin 1.8 mg/kg intravenously in combination with nivolumab 240 mg flat dose intravenously in a q 3 week cycle. In cycle 1, brentuximab vedotin 1.8 mg/kg will be administered on day 1 where as nivolumab 240 mg flat dose will be administered on day 8. Subsequent to cycle 1, both drugs will be administered on the first day of the new cycle. Brentuximab vedotin will be administered first as a 30-minute infusion followed by a minimum 30-minute rest. Nivolumab will be then be administered as a 30-minute infusion.

The DLT evaluation will be conducted in the first 6 treated subjects (all comers). Decisions to enroll up to 6 additional subjects onto the same dose of brentuximab vedotin 1.8 mg/kg in combination with nivolumab 240 mg flat dose intravenously every 3 weeks or at a reduced dose of brentuximab vedotin at 1.2 mg/kg will be based on the safety data reviewed throughout the DLT evaluation period. The DLT evaluation period consists of the first dose of study drug through the first 6 weeks of treatment.

If any of the first 6 treated subjects discontinue treatment for reasons other than a DLT, prior to completing the DLT evaluation period, then they will be replaced. These subjects will be monitored for DLT throughout the DLT evaluation period (DLT definition is provided further below in this section). After 6 DLT-evaluable subjects have been followed through the end of the DLT evaluation period, or at the point that 2 or more subjects experience a DLT, whichever comes first, the study team will review the available data. The BMS study team along with Seattle

Genetics study team and the investigators participating in the trial, will review all of the available safety data and provide any of the following recommendations that may include, but are not limited to:

1. One or none (≤ 1) of the 6 subjects experience a DLT, the expansion cohort will begin with brentuximab vedotin 1.8 mg/kg Cycle 1 Day 1 and nivolumab 240 mg flat dose on Cycle 1 Day 8. Subsequent to cycle 1, both drugs will be administered on the first day of the new cycle. Brentuximab vedotin will be administered first as a 30-minute infusion followed by a minimum 30 minute rest. Nivolumab will be then be administered as a 30 min infusion.
2. If two or more (≥ 2) of the 6 subjects are determined to have had a DLT based on the protocol definition, the following options will be considered
 - a. To repeat Cohort A of the study and treat up to 6 additional subjects at the same drug doses and schedule previously tested
 - b. To repeat Cohort A of the study and treat up to 6 additional subjects at a reduced dose of brentuximab vedotin 1.2 mg/kg;
 - c. Administration of the combination treatment on Day 1 of every cycle, including cycle 1
 - d. To close the study to additional enrollment.

NOTE: Doses may not be increased to above 1.8 mg/kg brentuximab vedotin or nivolumab 240 mg flat dose

On review of all available data, the study team may determine that the classification of DLT was not appropriate for one or more of the subjects, in which case enrollment may resume if the target of 6 DLT-evaluable subjects has not yet been reached. However, if 2 or more subjects were determined to have experienced DLTs, then expansion will not occur as the next step. Based on the study team's recommendations, up to 6 additional subjects may be enrolled in Cohort A at the same drug doses and schedule or at a modified treatment (described above in this section). These additional subjects will then be assessed for DLT in the same manner described above to determine if it is appropriate to move to the Expansion Phase (Cohort B). If it is determined by the study team that due to safety concerns no additional dose levels or schedules should be enrolled, then the study will be closed to enrollment.

Dose Limiting Toxicity

The incidence of dose limiting toxicities assessed in the first 6 DLT-evaluable subjects beginning Cycle 1 Day 1 through the first 6 weeks of treatment will determine whether the combination, nivolumab with brentuximab vedotin is tolerable. A subject will be considered evaluable for DLT if they have received at least one dose of either drug in the first 6 weeks of treatment. However, if the subject discontinues treatment for reasons other than a DLT prior to completing the DLT evaluation period, then they are **not** considered DLT evaluable and will be replaced. DLT should not be AEs considered by the investigator to be disease related. For the purpose of this study, DLTs are defined as any study drug-related toxicity (brentuximab vedotin or nivolumab) that requires either a dose reduction or delay of more than 7 days of either study drug in Cycle 2 or delays the Cycle 3 Day 1 administration of combined treatment by more than 7 days. The DLT evaluation period consists of the first dose of study drug through the first 6 weeks of treatment. The IBs for

brentuximab vedotin and nivolumab individually describe adverse events commonly observed relative to either agent (ie, neutropenia or peripheral neuropathy with brentuximab vedotin; immune-mediated adverse events with nivolumab), as well as less common serious findings. However, the final decision regarding causality is at the discretion of the Investigator.

There is no planned interim analysis (IA). However, all available efficacy and safety data will be used to select the recommended dose that will be further evaluated in the Expansion Phase (Cohort B).

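### DLT evaluability sets no minimum exposure to both drugs, so a subject with little or no combination exposure can count as DLT-free among the six who decide whether the combination is tolerable.

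*Protocol*

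**What the plan says.** Protocol section 4.5.1 states that the DLT incidence in the first six evaluable subjects "will determine whether the combination, nivolumab with brentuximab vedotin is tolerable". With at most one DLT in six, the expansion begins; section 8.1 plans 130 subjects for it.

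- **Evaluability.** A subject is "evaluable for DLT if they have received at least one dose of either drug in the first 6 weeks of treatment". The following sentence limits this: "if the subject discontinues treatment for reasons other than a DLT prior to completing the DLT evaluation period", the subject is not evaluable and is replaced. The same section states the replacement rule a second time.
- **Window.** "The DLT evaluation period consists of the first dose of study drug through the first 6 weeks of treatment".
- **Schedule.** The first cycle is staggered: "brentuximab vedotin 1.8 mg/kg will be administered on day 1 where as nivolumab 240 mg flat dose will be administered on day 8". From Cycle 2 both drugs are given on Day 1.
- **DLT.** A study-drug-related toxicity that "requires either a dose reduction or delay of more than 7 days of either study drug in Cycle 2", or that delays Cycle 3 Day 1 by more than 7 days.
- **Delays.** Section 4.5 allows a delay of up to 6 weeks from the previous dose. Section 4.5.5 allows longer non-drug-related delays with the medical monitor's approval. Sections 4.5.3 and 4.5.4.2 link the drugs: if one is delayed, so is the other, and the combination resumes on the first day of the next cycle.
- **Discontinuation in Cohort A.** If it is required within the window, both drugs stop (sections 4.5.3 and 4.5.5).

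SAP section 7.6.1 tabulates DLTs over all treated Cohort A subjects. Neither Protocol section 8.2 nor the published SAP section 6.3 lists a DLT-evaluable population.

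**The concern.** The quantity of interest is the DLT rate under both drugs, but the rule that admits a subject to the denominator requires only one of them. Discontinuation triggers replacement; a delay does not. A subject can therefore stay on study, receive little or none of the combination inside the window, and still count as one of the six without a DLT.

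Such a subject moves the observed rate towards the single-agent rate and makes the at-most-one-in-six rule easier to pass. With six subjects, each is a sixth of the evidence for opening the expansion, and Protocol section 7 provides for no data monitoring committee.

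**Working it through.** **1. The plan's own figures.** The one-sided 80% exact upper limit for x DLTs in n is the 0.80 quantile of Beta(x+1, n−x). For 1/6 it is 42.2% (Protocol section 8.1 states 42%). For 3/12 it is 41.2% (stated 41.2%). Both reproduce.

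**2. Route (a): no combination exposure.** Brentuximab vedotin is given on Day 1. Day 8 nivolumab and the later doses are then held for a non-drug-related reason. Six weeks from the Day 1 dose is Day 1 + 42 = Day 43, so the permitted delay spans the whole window (Days 1 to 42). The delay is not drug-related, so it is not a DLT. The subject has not discontinued, so there is no replacement.

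**3. Route (b): shortened exposure.** Section 4.5.4.1 delays nivolumab for, among others, drug-related non-skin events of Grade 2 or higher, with exceptions. An event in week 1 can therefore hold the Day 8 dose, and treatment resumes at Cycle 2 Day 1 (Day 22).

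- As scheduled: Days 8 to 42 = 35 days = 5 weeks on both drugs, with two nivolumab doses before Cycle 3.
- After the hold: Days 22 to 42 = 21 days = 3 weeks, half the window, with one nivolumab dose before Cycle 3.

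The first nivolumab dose is 14 days late, but the dose missed belongs to Cycle 1. The delay criteria in the DLT definition name Cycle 2 and Cycle 3 Day 1, so this hold is not a DLT on the text as written.

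**4. Size of route (a).** Let p be the combination DLT rate and q the single-agent rate; both are assumptions. With all six exposed,

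P(pass) = (1−p)^6 + 6p(1−p)^5.

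With one subject on a single agent,

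P(pass) = (1−q)·[(1−p)^5 + 5p(1−p)^4] + q·(1−p)^5.

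- p = 0.40, six exposed: 0.0467 + 0.1866 = 0.233. One unexposed, q = 0.10: 0.9 × 0.3370 + 0.1 × 0.0778 = 0.311.
- p = 0.30, six exposed: 0.1176 + 0.3025 = 0.420. One unexposed, q = 0.10: 0.9 × 0.5282 + 0.1 × 0.1681 = 0.492.

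Range over q, with one unexposed subject:

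| q | p = 0.30 (42.0% if all exposed) | p = 0.40 (23.3% if all exposed) |
|---|---|---|
| 0 | 52.8% | 33.7% |
| 0.05 | 51.0% | 32.4% |
| 0.10 | 49.2% | 31.1% |
| 0.20 | 45.6% | 28.5% |

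**5. Effect on the stated precision.** If one of the six was unexposed and the single DLT fell in an exposed subject, the combination evidence is 1/5. Its upper limit is 49.0%, against 42.2% for 1/6.

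**6. Route (b) is outside this model.** These subjects receive both drugs, so the table does not apply to them. What matters there is classification: the rule tolerates one DLT, so whether one toxicity-related Day 8 hold is counted can separate 1/6 from 2/6.

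**The case against.** The strongest reply is that the evaluability sentence should not be read alone. The next sentence removes and replaces anyone who discontinues for a non-DLT reason. Single-agent continuation after a required discontinuation is barred in Cohort A during the window, and linked delays mean that a subject who misses only Day 8 is due both drugs on Day 22. Drug-related toxicity that delays Cycle 2 by more than 7 days is a DLT. All of this stands. It rules out the stronger reading a reader might take from the evaluability sentence, that any subject with a single dose who then leaves counts as clean.

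It does not close routes (a) and (b), because both run through delay rather than discontinuation. Route (a) is narrow: Day 8 must be missed and Cycle 2 then held through week 6 for a non-drug-related reason.

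A second reply is that the count is not the only input. The two companies' study teams and the investigators review all available safety data, and SAP section 7.4.1 provides a by-subject dosing listing, so an unexposed subject would be visible. That is a real mitigation, but nothing tells the reviewers to set such a subject aside, and the rule for starting the expansion is written as a count in six.

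A third reply is that the rates are assumed and that large effects need several unexposed subjects. That also stands. Two or three unexposed subjects would give 41% or 53% at rates of 40% and 10%, but nothing in the documents makes that plausible. One is the realistic case.

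**Conclusion.** The concern holds in a limited form. The evaluability rule sets no minimum exposure to both drugs, and two delay routes let a subject count as DLT-free with no combination exposure in the window, or with three weeks instead of five.

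For one unexposed subject in six, the chance of passing rises by about 7 to 8 percentage points at an assumed 10% single-agent rate (23% to 31%, or 42% to 49%). Over single-agent rates from 0 to 20%, the rise is about 4 to 11 points. The documents give neither the DLT rates nor the number of such subjects. They do not show that any subject in Cohort A took either route, and they do not support inferring that the dose decision was wrong.

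The SAP denominator adds a separate problem. Tabulating over all treated Cohort A subjects would bring replaced subjects, including any who had one drug only, back into the reported rate.

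**What to change.** In Protocol section 4.5.1, define DLT-evaluable as either having had a DLT, or having received both drugs with a stated minimum combination exposure and follow-up to the end of the window.

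Replace a DLT-free subject only when the shortfall is not drug-related. Keep subjects whose doses were withheld for drug-related toxicity in the denominator. Requiring every scheduled dose and replacing everyone else would remove exactly those subjects and hide toxicity.

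Reconcile how a toxicity-related Day 8 hold is classified against the DLT definition. At the same time, reconcile that definition, which does not name discontinuation, with SAP section 7.6.1, which adds it. The clinical choice belongs to the study team.

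Add the DLT-evaluable set to SAP section 6.3, use it as the denominator in section 7.6.1, and list each Cohort A subject's exposure to each drug beside DLT status.

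The cost is a few sentences, one analysis set, one listing and possibly one replacement subject. SAP section 7.1 describes Cohort A's dose exploration in the past tense. If Cohort A is complete, replacement may no longer be possible, but the SAP set and listing can still be applied and would show whether the six subjects support the conclusion.
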